5.5.2 Randomisation and Blinding

This study will not involve randomisation. Due to the titration aspect of the preceding double-blinded study (SAG/0211PFC-1131), bottles will not specifically identify whether they contain lubiprostone 12 or 24 mcg so as to maintain the prior blind. Dose assignment will be based on the dose they were receiving at the time of rolling over from the preceding, double-blind study (SAG/0211PFC-1131) into this safety extension study for those subjects who were randomised to receive lubiprostone during the preceding study. For subjects who received placebo during the preceding study (as identified via IXRS), assignment of dose by the IXRS will be based on subject body weight at the time of rollover to this extension study. Dose assignment will only be known in subjects who were at least 50 kg in weight at the time of randomisation in the preceding study (SAG/0211PFC-1131). All dose assignments will be handled by the IXRS and will continue to maintain blinding with respect to the treatment assignment in the preceding trial.

Most study personnel will remain blinded to doses assigned to subjects weighing less than 50 kg until the clinical database has been locked. To allow for the execution of clinical trial-related services, the following individuals will be unblinded during the study:

- External RTSM vendor
- Sponsor Quality Assurance representative
- Sponsor Pharmacovigilance representative
- External clinical supply distribution vendor

- External third party unblinded biostatistician (e.g., DSMB statistician)
- DSMB members
- Bioanalytical laboratory and third-party pharmacokinetic analyst
- Sponsor Drug Supply Management representative

Emergency unblinding by the Investigator of a subject's assigned treatment is addressed in [Section 4.6](#) of this protocol.

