8.5.2 Adverse Events

The original terms used in the eCRF by Investigators to identify AEs will be coded to MedDRA® system organ class and preferred terms. Adverse events will be summarized in terms of incidence per dose group and overall. The incidence of an AE is defined as the number of subjects who experienced at least one episode during the study. Adverse event incidence rates will be summarized by system organ class (SOC) and preferred term (as determined by the coding).

Whatever the level of classification, if a subject experiences multiple episodes of an event within the given time reference, then the event is only counted once. Further, for summaries by severity or causality, the most severe event is chosen for a subject if that subject experiences multiple episodes of the same event.

In this study, faecal impaction and bone fractures will be captured as AEs. The events of faecal impaction will be used for the analysis of the faecal impaction frequency during the study (see [Section 8.6.2.6](#)).

AEs with onset dates after administration of the first dose of study medication or prior to the last day of treatment + 7 days will be considered treatment-emergent. Events with completely or partially missing onset dates will be included in the tabulations, unless the available partial date information clearly indicates that the event happened outside of the treatment period.

P-values from Fisher's exact test or chi-square test will be presented in the AE summary tables. The test will be performed to compare incidence rates at the SOC and "At Least One Event" level between the two treatment groups.

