8.6 Analysis of Efficacy

8.6.1 General Inferential Principles

The following principles apply for all inferential analyses of efficacy: All tests are two-tailed at a significance level of $\alpha = 0.05$.

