8.6.2.7 Overall and Monthly Change from Baseline in Constipation Signs and Symptoms

Mean changes from baseline will be generated based on subject reported data as to the degree of:

- Straining associated with SBMs;
- Stool consistency of SBMs;
- Abdominal pain associated with SBMs; and
- Constipation severity.

The following rating scales will be used:

Stool consistency: Modified Bristol Stool Form Scale (5-point scale);

Bowel straining: 0=Not at all, 1=A little, 2=Some, 3=Quite a bit, 4=Extremely

Constipation severity and abdominal pain: 0=Absent, 1=Mild, 2=Moderate, 3=Severe, 4=Very severe.

The overall change from baseline will be calculated as the baseline value subtracted from the average of all diary ratings, where the baseline value will represent the average rating during the 2-week screening period of the previous study (SAG/0211PFC-1131). The change from baseline for a week (7-day period) or month (4-week period) will also be calculated as the baseline value subtracted from the average of all diary ratings during a week or month.

Stool Consistency

The analysis of stool consistency will focus on consistency assessments associated with SBMs. The average stool consistency rating will be calculated for each month (4-week period), excluding measurements recorded within 24 hours after rescue medication intake.

Analyses will be based on the change from baseline, where the baseline value will represent the average stool consistency rating from all SBMs during the 2-week screening period of the previous study (SAG/0211PFC-1131). The van Elteren test using the change from baseline stratified by pool centre and stratified by study for the pooled group will be used.

Straining

Bowel straining will be analysed in a method similar to stool consistency.

Constipation Severity

The changes from baseline in mean constipation severity ratings at each month during Months 1 through 9 will be analysed. The change from baseline will be calculated as the baseline value subtracted from the average of all diary ratings during the given month. For these daily diary assessments, each month will be defined by 4-week intervals beginning with the day of the first dose of study medication (Day 1). For example, Month 1 will start with the daily assessment on Day 1 and end with the daily assessment on Day 29 (Week 4), Month 2 will start with the daily assessment on Day 30 and end with the daily assessment on Day 57 (Week

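### The dose groups are not randomised, so the unadjusted AE p-values in 8.5.2 cannot be read as dose effects; the van Elteren tests name no comparison groups

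*Combined protocol and SAP*

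**What the plan says.** **Allocation.** Section 5.5.2 states "This study will not involve randomisation". For prior-lubiprostone subjects, "Dose assignment will be based on the dose they were receiving at the time of rolling over". For prior-placebo subjects, "assignment of dose by the IXRS will be based on subject body weight at the time of rollover to this extension study". The same section says that bottles do not show the strength, "Due to the titration aspect of the preceding double-blinded study". The site knows the dose only for subjects who weighed at least 50 kg at randomisation in the preceding study. Section 3 repeats these rules and gives about 415 subjects.

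**Adverse events.** Section 8.5.2 summarises incidence per dose group and overall. It adds p-values from Fisher's "exact test or chi-square test will be presented in the AE summary tables", at SOC level and for any event, between two treatment groups that it does not define. It mentions no stratification or adjustment and does not call the p-values descriptive. Safety is the primary objective (Section 2.1).

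**Efficacy.** Section 8.6.1 says of efficacy inference: "All tests are two-tailed at a significance level of" 0.05. For stool consistency, Section 8.6.2.7 says: "The van Elteren test using the change from baseline stratified by pool centre and stratified by study for the pooled group will be used". The constipation-severity text is similar, and straining and abdominal pain follow the same methods. Section 8.6.2.8 applies van Elteren, stratified by pooled centres, to SBM frequency rates. None of these paragraphs says which groups are compared.

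**The concern.** A p-value beside two dose columns invites the reader to take a small value as a dose-related harm and a large one as reassurance. Neither reading is safe here. Whether a child is in the 12 or the 24 mcg column depends on body weight, on how the child fared under earlier titration, and on which of two assignment rules applied, which itself depends on prior treatment. Age comes in through weight, over a range of 6 to under 18 years. Any of these may affect AE incidence, and the planned tests account for none of them. These p-values would stand in the tables for the primary objective.

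The efficacy problem is different. The symptom endpoints are changes from baseline in subjects who all receive lubiprostone. Van Elteren is a stratified rank test between independent groups. With no groups named, the test is undefined. With groups named, it would compare them and still give no inference on the change itself.

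**Working it through.** **The plan's own figure.** The 415 cannot be reproduced. Section 8.1 rests it on expected attrition and gives no attrition rate, target, effect size or power.

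**Inputs from the protocol.** About 415 subjects (Section 3); no randomisation and two assignment rules (5.5.2); unadjusted Fisher or chi-square (8.5.2).

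**Assumed inputs.** The documents give no AE rates, dose split or weight mix, and do not say which dose heavier subjects receive. Section 8.5.2 states no significance level, so two-sided 5% is used. Assume no dose effect, 208 subjects on 12 mcg and 207 on 24 mcg, AE incidence 20% in lighter and 30% in heavier children, a 12 mcg group that is all lighter, and a 24 mcg group that is 70% heavier.

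**Step 1: incidence by group.**
- p12 = 0.20
- p24 = 0.70 × 0.30 + 0.30 × 0.20 = 0.27

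The 7-point gap comes from weight alone.

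**Step 2: chance of rejection.**
- Pooled incidence = (208 × 0.20 + 207 × 0.27)/415 = 0.235
- SE under equality = √[0.235 × 0.765 × (1/208 + 1/207)] = 0.0416
- SE under the actual incidences = √[0.20 × 0.80/208 + 0.27 × 0.73/207] = 0.0415
- Rejection ≈ Φ[(0.07 − 1.96 × 0.0416)/0.0415] = Φ(−0.28) = 0.39

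Exact enumeration of Fisher's test gives 0.38.

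**Step 3: other inputs (Fisher, exact, no dose effect).**

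| Incidence, lighter / heavier | 24 mcg group 70% heavier | 24 mcg group 100% heavier |
|---|---|---|
| 20% / 30% | 0.38 | 0.64 |
| 50% / 55% | 0.11 | 0.17 |
| 20% / 20% | 0.04 | 0.04 |

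The right-hand column is a bound, not a realistic case. Dose is blinded below 50 kg, which implies that both doses occur there.

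**Step 4: a mix with lighter children on both doses.** Suppose 166 of 415 subjects (40%) are heavier and all take 24 mcg. Of the 249 lighter subjects, 75 (30%) take 24 mcg. This gives 174 on 12 mcg and 241 on 24 mcg. Let incidence be 60% in lighter and 50% in heavier subjects, with no dose effect.
- p12 = 0.60
- p24 = (166 × 0.50 + 75 × 0.60)/241 = 0.531
- Simulated rejection (20,000 runs, unadjusted two-proportion test): 28.8%
- The same test in lighter subjects only: 5.2%
- With no weight dependence: 5.1%

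The 5.2% shows only that the weight bias has gone. Selection by earlier titration was not modelled.

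**Step 5: masking.** Keep that mix and add a true 10-point increase on 24 mcg.
- p12 = 0.60
- p24 = (166 × 0.60 + 75 × 0.70)/241 = 0.631

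The visible gap shrinks from 10 points to about 3. Rejection falls to 10%, against 53% for the same dose effect when incidence is 50% in both weight groups.

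**Step 6: van Elteren.** Sections 8.6.2.7 and 8.6.2.8, set beside Section 2.2.2, show three gaps:
- No comparison groups are named.
- Section 8.6.2.7 refers to individual studies and a pooled group that this single-study protocol does not define. The Synopsis considers safety data together with SAG/0211PFC-11S2, and Section 8.5.8 mentions pooled pivotal data, but neither defines an efficacy pooling.
- Mean changes from baseline are planned, but Section 8.6.2 gives no interval or within-subject test for them.

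**The case against.** Several points on the other side stand.

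- **Decision role.** Nothing in the plan turns on these p-values. There is no success criterion, the sample size rests on attrition, and AE incidence is also reported overall, which serves the safety objective directly. This lowers the severity.
- **The test itself.** Fisher's test does not assume comparable groups. It tests equality of two incidences, and in the scenarios above they do differ. The 38% is a fault only if the result is read as a dose effect.
- **Deferred detail.** Section 8 defers detail to an SAP that is not in the supplied text. It may add strata or a descriptive label. The protocol as written still specifies the tests without either.

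A reader might also infer more than the documents support.

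- One might say that the p-values test weight and age and carry no information about dose. Dose also differs between the groups, so it is confounded, not absent. Blinding below 50 kg implies that dose and weight are not fully collinear, and age is not an assignment variable.
- One might say that van Elteren compares 12 with 24 mcg. The text names no groups, and the missing comparator is the defect.
- One might quote 64% as the error rate. It needs a 24 mcg group with no lighter children, which the blinding arrangement contradicts.

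**Conclusion.** The concern holds in this limited form. As written, Section 8.5.2 yields unadjusted p-values between non-randomised groups, with no caution attached. They mix dose with weight, titration history and prior treatment, so neither a significant nor a non-significant result can be attributed to dose. That the two groups are the dose groups is the natural reading of 8.5.2, not an explicit statement.

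The illustrative size is about 38% rejection with no dose effect, against a nominal 5%, and near 5% if incidence does not depend on weight. It rests wholly on assumed incidences and an assumed dose and weight mix. The direction is also open: the same mechanism can hide a real difference. Separately, the van Elteren tests lack a defined comparison and leave within-subject change without inference.

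Severity is should-fix, because no decision rule or sample size depends on these results.

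**What to change.** **Section 8.5.2.** Define the groups. Remove the between-dose p-values, or label them descriptive and non-randomised. Report AE incidence with exact 95% confidence intervals overall, by dose, and by weight stratum and prior treatment (placebo or lubiprostone). Use one named weight for the strata, such as weight at rollover, because Section 5.5.2 uses weight at two different times. State that stratification does not remove selection by earlier titration, and that a stratum holding only one dose gives no dose contrast. The latter may be so at 50 kg and above.

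**Sections 8.6.2.7 and 8.6.2.8.** Replace van Elteren with within-subject change from baseline and its 95% confidence interval, with a signed-rank test if a test is wanted. Give responder proportions with exact 95% confidence intervals. Present both overall, and by dose descriptively. Delete the stratification by study for a pooled group.

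**Cost.** Protocol and SAP text and table shells; trial conduct and data collection do not change. The sponsor gives up dose p-values that cannot be read as dose effects.

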8.5.3 Clinical Laboratory Tests

For clinical laboratory data, mean changes from pre-treatment to post-treatment visits will be summarized using descriptive statistics. Cross-tabulations analysis will be performed for laboratory parameters with reference normal ranges. The laboratory data will be categorized as low, within, and above the reference normal ranges. The summary tables will tabulate the number and percentage of subjects with pre-treatment values below/within/above the normal reference range versus minimum/maximum/final post-treatment values below/within/above the normal reference range. Normal reference ranges will also be provided in the summary display. Laboratory parameters that are not specified in the protocol will not be included in the analysis, but they will be provided in the individual subject listings.

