Sample Size Estimate Calculation	
For purposes of establishing the safety profile with lubiprostone long-term exposure in paediatric functional constipation, safety data from subjects enrolled in this study will be considered together with the 100 subjects enrolled in Sucampo study SAG/0211PFC-11S2 (subjects in this study will be below 6 years old).
 
The sample size is based on the expected attrition that would occur and the remaining number of safety evaluable subjects at each timeframe during the study.

Statistical Methodology	
Efficacy analysis will be based on modified intent-to-treat (mITT) population which includes all enrolled subjects who take at least one dose of study medication and have at least one treatment period diary entry. Categorical and discrete variables will be summarized by counts and percentage, and continuous variables will be summarized by descriptive statistics. Detailed statistical methodology will be documented in the Statistical Analysis Plan (SAP).
 
Adverse events will be summarized in terms of incidence by treatment group and overall. Changes from baseline or clinical abnormalities in clinical laboratory data, physical examinations, and vital signs will be summarized by treatment group and overall.
 
The PK profile for lubiprostone will be determined from the concentration-time data for all evaluable subjects based on the plasma concentrations lubiprostone (if measurable) and of lubiprostone's metabolite, M3. Actual post-dose sampling times relative to time of study medication administration, rather than scheduled sampling times, will be used in all PK profile computations involving sampling times.

SCHEDULE OF EVALUATIONS

Study Week(s) / Month(s)	0	1 / 0	4 / 1	12 / 3	16 / 4	24 / 6	28 / 7	36 / 9	40 / 10
Study Day(s)	1	8 (± 2)	29 (± 3)	85 (± 3)	113 (± 3)	169 (± 3)	197 (± 3)	253 (+ 3)	281 (+ 3)
Visit Number	9	10	11	12	13	14	15	16	17
Visit Type	Enrolment ¹	Clinic Examination	Telephone Assessment	Clinic Examination	Telephone Assessment	Clinic Examination	Telephone Assessment	End-of-Treatment Clinic Examination	Follow-up Clinic Examination
Assessment									
Informed Consent/Assent	X								
Inclusion/Exclusion Criteria Review	X								
Demographics	(V1)								
Medical History	(V1/V2)								
Vital Signs, Height, and Weight ²	(V7)	X		X		X		X	X
Physical Examination ³	(V7)	X		X		X		X	X
Pharmacokinetic Sampling ⁴	X								
Blood Chemistry, Hematology, Urinalysis	(V7)	X		X		X		X	X

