6.3 Safety Evaluations

The following safety evaluations will be performed during the study to measure the safety of the study medication:

Adverse Events: AEs will be reported by the subject from the time of informed consent through the end of the follow-up period. AEs will be followed by the Investigator as determined by Sponsor or designee. Further details on AE reporting are provided in [Section 7](#). Any study medication related AEs persisting at the end of the study will be followed until resolution, or until a clinically stable endpoint has been reached.

In this study, faecal impaction and bone fractures will be captured as AEs. The events of faecal impaction will be used for the analysis of the fecal impaction frequency during the study (see [Section 8.6.2.5](#)).

Clinical Laboratory Tests: The following laboratory tests will be conducted and the appropriate Investigator shall determine the clinical significance of any out-of-range values.

- **Hematology Panel:** Hemoglobin, hematocrit, MCV, MCH, MCHC, RBC, WBC, white blood cell with absolute counts and percent differentials (neutrophils, lymphocytes, monocytes, eosinophils, basophils), platelet count.
- **Chemistry Panel:** Total cholesterol, triglycerides, glucose, total protein, albumin, alkaline phosphatase, AST, ALT, GGT, iron, LDH, total bilirubin, direct bilirubin, BUN, uric acid, creatinine, sodium, potassium, chloride, bicarbonate, calcium, phosphorus, magnesium.
- **Urinalysis:** Protein, glucose, ketones, occult blood, pH, specific gravity, color, appearance, leukocyte esterase, nitrite, bilirubin, and macroscopic examination. Microscopic examination will be done if abnormalities are present. Urine samples will be collected, when possible.

Physical Examination: Physical examinations will be conducted at various timepoints during the study. Any new post treatment findings or changes, as noted by the Investigator, will be reported as an AE.

Vital Signs:

Vital signs (including height and weight at designated visits) will be recorded during the study. Any post treatment clinically significant changes in vital signs (including weight) shall be noted by the Investigator and reported as an AE. Additional guidance regarding assessment of changes in blood pressure and heart rate are provided below.

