7.2.1 Reporting of Immediately Reportable Events

The following events, regardless of severity or seriousness, are considered immediately reportable IREs and are to be reported via the IRE Form within 24 hours to the Sponsor or designee:

- All Serious Adverse events;
- All pregnancies; and
- Events of Special Interest (list all events of special interest).
 - Chest pain/chest discomfort
 - Dyspnea/shortness of breath/difficulty breathing
 - Hepatotoxicity/liver enzyme increased
 - Anaphylaxis, including anaphylactoid reaction and anaphylactic shock

Immediately Reportable Events, such as SAEs, should be recorded on the Adverse Event source document and eCRF. In addition, any IRE occurring during the clinical study must be reported within 24 hours to the Sponsor or designee using the IRE form. The initial report of an IRE must be documented on the study IRE form, signed by the Investigator and submitted by facsimile. The Investigator must provide the following information: protocol number,

subject's initials and study number AE term and associated dates, causal relationship between the event and study medication, relevant history, study medication dosing details, full description of the event, and other required data within the IRE form. All oral reports of an IRE must be followed immediately by a facsimile of the IRE form signed by the Investigator. Investigators should not leave oral reports of IREs on any voicemail aside from the Sponsor's Medical Monitor or designee. The details of the adverse event reporting requirement are also outlined in a safety reporting plan.

The Sponsor assumes responsibility for reporting of expedited and periodic safety reports to the appropriate regulatory authorities. The Sponsor will report to the Investigator any new safety events occurring in other studies. The Investigator may need to report SAEs to the appropriate IRB/IEC in accordance with local regulations.

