7.2.4 Clinical laboratory evaluations

A change in the value of a safety laboratory investigation can represent an AE if the change is clinically relevant or if, during treatment with the investigational product, a shift of a parameter is observed from a normal value to a pathological value, or a further worsening of an already pathological value. When evaluating such changes, the extent of deviation from the reference range, the duration until return to the reference range, either while continuing treatment or after the end of treatment with the investigational product, and the range of variation of the respective parameter within its reference range, must be taken into consideration.

If, at the end of the treatment phase, there are pathological laboratory values which were not present at baseline, per investigator discretion further clinical or laboratory investigations should be performed until the values return to within reference range or until a plausible explanation (e.g., concomitant disease) is found for the pathological laboratory values.

The Investigator should decide, based on the above criteria and the clinical condition of a subject, whether a change in a laboratory parameter is clinically significant and therefore represents an AE.

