8.8 Data Collection

Original source data will be collected via source documents. Final data for this study will be collected using electronic case report forms (eCRFs). Data must be entered onto the eCRFs in English. All eCRFs must be completed in a timely manner before the Sponsor or designee performs a monitoring visit. The Principal Investigator will be required to electronically sign the eCRFs casebook for each subject. Laboratory reports must be reviewed, signed, and dated by an appropriate Investigator and filed with the source documents. Any laboratory findings out of the normal range should indicate the clinical significance (clinically significant [CS] or not-clinically significant [NCS]) of the results on both the source document and the corresponding eCRF.

The eCRFs are to be completed as soon as possible from the time of the subject's visit, with the exception of results of tests performed outside the Investigator's office, so that they always reflect the latest observations on the subjects participating in the study.

All eCRF corrections are to be made or reviewed by the Investigator or other authorized study site personnel.

Automatically generated queries will be answered by site personnel during the eCRF completion process.

The dates of the monitoring visits will be recorded by the monitor in a study site visit log to be kept at the site. The first post initiation visit will usually be made as soon as possible after enrolment has begun. At these visits, the monitor will compare the data entered into the eCRFs with the hospital or clinic records (source documents). Source documentation must be available to substantiate proper informed consent procedures, adherence to protocol procedures, adequate reporting and follow-up of AEs, administration of concomitant medication, medication receipt/dispensing/return records, and study medication administration information. Specific items required as source documents will be reviewed with the Investigator prior to the study. Findings from this review of eCRFs and source documents will be discussed with the Investigator. The Sponsor expects that, during monitoring visits, the Investigator and study coordinator, will be available, the original source documentation, regardless of media, will be available, and a suitable environment will be provided for review of study-related documents.

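### The laboratory shift tables in Section 8.5.3 are cut only at the reference range, so for liver tests they neither count children by size of rise nor show worsening from a high baseline

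*Combined protocol and SAP*

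**What the plan says.** Section 8.5.3 plans two summaries of laboratory data.

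- **Change in level:** "mean changes from pre-treatment to post-treatment visits will be summarized using descriptive statistics". The section does not list which statistics.
- **Shift tables:** "The laboratory data will be categorized as low, within, and above the reference normal ranges". The pre-treatment class is then tabulated "versus minimum/maximum/final post-treatment values below/within/above the normal reference range".

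Other parts of the protocol bear on the liver tests:

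- Section 2.1 makes safety the primary objective.
- The chemistry panel in Section 6.3 includes "alkaline phosphatase, AST, ALT, GGT, iron, LDH, total bilirubin, direct bilirubin". Section 6.1.1 sends samples to a central laboratory and applies paediatric ranges appropriate to age.
- Section 7.2.1 lists "Hepatotoxicity/liver enzyme increased" among the events of special interest to be reported within 24 hours. It gives no numeric threshold.
- Section 7.2.4 allows a shift from a normal to a pathological value, "or a further worsening of an already pathological value", to count as an adverse event if the investigator so judges.
- Section 8.8 adds: "Any laboratory findings out of the normal range should indicate the clinical significance". No tabulation of that flag is described.
- The Protocol Synopsis, under Statistical Methodology, promises: "Changes from baseline or clinical abnormalities in clinical laboratory data, physical examinations, and vital signs will be summarized by treatment group and overall". It does not define a clinical abnormality.

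Section 8 refers to a SAP to be finalised before database lock. Its text is not part of the material reviewed here.

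**The concern.** With one cut-off on each side, the shift table records that a child crossed the upper limit but not by how much. For aminotransferases the size of the rise is the informative part. Small excursions above range are expected in any large set of repeated samples, and a few large ones are what a hepatic safety review looks for. The table merges the two, and it cannot show movement in a child who starts above range.

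This matters more here than in a controlled trial. Section 5.5.2 says the study is not randomised, and every subject receives lubiprostone, so there is no placebo rate of above-range values to compare against. The adverse event route does not supply the missing scale either. Section 7.1.3 grades severity by symptoms, interference with daily activities and need for intervention, so a large rise without symptoms need not be graded severe. Section 8.5.2 describes no separate table for events of special interest.

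**Working it through.** The plan states no figure on this point, so there is none to reproduce. The check applies the Section 8.5.3 rule to example values and then asks whether the mean-change summary fills the gap.

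**1. The rule applied to example values** (assumed values, in multiples of ULN)

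| Baseline | Post-treatment maximum | Shift-table cell |
|---|---|---|
| 0.6 | 1.05 | within to above |
| 0.6 | 3.5 | within to above |
| 0.6 | 10 | within to above |
| 1.2 | 1.05 (a fall) | above to above |
| 1.2 | 1.25 | above to above |
| 1.2 | 10 | above to above |

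The first three rows share one cell, and so do the last three. This follows from the classification itself and needs no assumption about how often such values occur.

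**2. Does the mean show it?** Planned enrolment is 415 (Protocol Synopsis; Section 3). If k children rise by r and the rest do not change, the mean moves by k × r / 415.

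- One child, r = 2 to 9 × ULN: 2/415 = 0.005 to 9/415 = 0.022 × ULN.
- Four children, same range: 8/415 = 0.019 to 36/415 = 0.087 × ULN.
- Four children (about 1%), r = 200 U/L: 4 × 200/415 = 1.9 U/L.

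The last figure is for all subjects together. If all four were in one dose group of n children it would be 800/n, for example 3.9 U/L if that group were half of 415 (800/207.5). The documents do not give the group sizes.

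**3. How many small excursions could surround them?** The Schedule of Evaluations has four on-treatment samples after enrolment (Visits 10, 12, 14 and 16). Assume a 2.5% chance per sample of exceeding the upper limit, independence between samples, and no dropout.

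- Four samples: 1 − 0.975⁴ = 9.6%, and 0.096 × 415 ≈ 40 children.
- Counting Visit 17 as well: 1 − 0.975⁵ = 11.9%, or about 49 children.

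Positive correlation between samples from the same child would lower both counts, as would dropout. In the shift table, the four marked cases would be indistinguishable from these.

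**4. Would other descriptive statistics show it?** Section 8.3 lists mean, median, standard deviation, minimum and maximum for subject characteristics. If the same set is used for laboratory change, the four children alone contribute √(4/415 × 411/415) × 200 ≈ 19.5 U/L to the standard deviation. With an assumed background standard deviation of 10 U/L, the total is √(10² + 19.5²) ≈ 22 U/L, and the maximum change would be about 200 U/L. A careful reader would see that something was there, but not how many children were affected or which of them began above range.

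**The case against.** The strongest reply is that Section 8.5.3 is an outline. The synopsis leaves detailed methodology to the SAP and commits to summarising clinical abnormalities, and a graded definition is ordinary SAP content. This stands in part: the finding can apply only to the plan as documented in the protocol. However, Sections 8.5.5, 8.5.8, 8.6.1.1 and 8.6.1.3 each pass detail to the SAP explicitly. Section 8.5.3 does not, and it sets out its tables as the analysis.

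A reader might infer that the plan would hide a marked liver-enzyme rise altogether, or that there is no measured magnitude against which to check adverse event reports. The documents do not support that. Central-laboratory values will exist for sampled subjects, and out-of-range results carry a clinical-significance flag. Section 7.2.4 tells the investigator to weigh how far a value departs from the range. Liver events are reported within 24 hours and enter the incidence tables, serious events and adverse terminations are listed by subject, and an unblinded DSMB reviews safety. The descriptive statistics may also expose an extreme value. These routes reveal individual cases, several of them through investigator judgement. None gives a pre-specified count by size.

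It is also fair to say that the numerical illustration takes only 415 and the number of samples from the documents, and that the graded table could be produced later from stored data. Both points are accepted. The first means that the numbers do not carry the argument. The second means that little is lost, although cut-points chosen after the data are seen are less convincing than cut-points fixed beforehand.

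**Conclusion.** The point holds as a limitation of the categorical laboratory tables. As Section 8.5.3 is written, the shift tables for ALT, AST and bilirubin cannot count subjects by size of rise and cannot show worsening from an already high baseline. No other documented output supplies a pre-specified count by magnitude, and the synopsis term for clinical abnormalities is left undefined. This conclusion rests only on the stated classification, subject to whatever the SAP adds.

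The 1.9 U/L shift and the 40 children are illustrative. The 1%, 200 U/L, 2.5% and independence inputs are assumptions, not document figures. No claim is made that a hepatic signal exists or would be missed. The point is a minor, inexpensive improvement to the primary safety reporting.

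**What to change.** In Section 8.5.3, or in the SAP before database lock, add the following.

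- **One table, by dose group and overall:** maximum on-treatment ALT and AST in multiples of the central laboratory's age-specific ULN (for example >1–3, >3–5, >5–10, >10) and maximum total bilirubin (for example >2), cross-classified by the same categories at baseline. Include a count of subjects with aminotransferase and bilirubin raised together.
- **One listing:** the subjects in those categories, beside whether a liver event of special interest was reported.
- **One definition:** state that these categories are what the synopsis means by clinical abnormalities for liver tests, or define that term otherwise.

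The documents give no thresholds, so the bands above are examples. They are display categories for the sponsor to set, not limits for clinical action, and they change no management rule. The cost is one table and one listing from data already collected, with no change to visits, samples or conduct.
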